1.6.2. Use of a Placebo Control

This study uses placebo as a comparator on the background of standard of care treatment. Placebo was chosen as the control because it is necessary to determine the efficacy, safety, and tolerability of voxelotor by allowing safety signals to be distinguished from AEs occurring due to SCD.

With the exception of the initiation of HU during screening or after randomization and chronic transfusion, all approved therapies for SCD are allowed under this protocol. This includes analgesics, HU, and L-glutamine, according to the local standard of care.

Randomization to placebo treatment in this study does not place study participants at increased risk, as the standard of care for patients with conditional TCD flow velocities is continued observation, including repeat TCD assessments.

2. STUDY OBJECTIVES

See Section 3 for details regarding the investigational plans.

2.1. Primary Objective

The primary objective is to evaluate the effect of voxelotor compared to placebo on the TCD time-averaged mean of the maximum velocity (TAMMV) arterial cerebral blood flow at 24 weeks in SCD participants ≥ 2 to < 15 years of age with conditional (170 to < 200 cm/sec) TCD flow velocity.

2.2. Secondary Objectives

The secondary objectives are to evaluate the effects of voxelotor compared to placebo on:

- Change in TCD flow velocity at Week 48 and Week 96
- Conversion of TCD category from conditional to abnormal
- · Reversion of TCD category from conditional to normal
- · Proportion of participants with TCD response
- Change in Hb over time
- Change in clinical measures of hemolysis
- Annualized incidence rate of vaso-occlusive crises (VOCs)

2.4. Safety Objective

The safety objective is to assess the safety and tolerability of voxelotor compared to placebo.

2.5. Pharmacokinetic Objective

The pharmacokinetic (PK) objective is to assess the PK of voxelotor as evaluated by PPK analysis.

3. INVESTIGATIONAL PLAN

This multicenter SCD study is a randomized, placebo-controlled, double-blind, prospective study of the efficacy and safety of voxelotor in pediatric participants ≥ 2 to < 15 years of age.

3.1. Study Endpoints

Study endpoints are described in Section 8.

3.1.1. Study Design

The study will be conducted globally at approximately 50 clinical sites. Study procedures and assessments are outlined in Section 6. The timing of these procedures and assessments are provided in Appendix A, Appendix B, and Appendix C. Dosage and treatment administration are outlined in Section 5.

The study consists of 3 periods (Figure 1):

- · Screening: up to 35 days prior to randomization
- Treatment: 96 weeks
- Follow-Up: 28 days (4 weeks) after the last dose

Approximately 224 participants aged 2 to < 15 years will be randomized 1:1 to voxelotor or placebo.

Participants \geq 12 years old will be administered a fixed dose of voxelotor 1500 mg/day. Participants younger than 12 years of age will receive voxelotor at a weight-based (1500 mg-equivalent) dose, as described in Section 1.6 (Table 1).

Following completion of study treatment, eligible participants will be given the option to enroll in an open label extension study (under a separate protocol) to receive voxelotor for a minimum of 3 years (3 years or until commercial product becomes available or a managed access program, whichever is longer).

At the time of randomization, participants will be stratified by HU use (yes; no), age (2 to ≤ 8 years; > 8 to < 15 years), Screening TCD flow velocity value (170 to < 185 cm/sec; 185 to < 200 cm/sec), and geographic region (Africa including Middle East and North Africa [MENA]; rest of world). Stratification of participants by age was chosen to evenly balance by age distribution using the expected median age of 8 years.

Figure 1: Study Schema

Abbreviations: EOT, end of treatment. Note: Primary endpoint will be assessed at Week 24.

In this study, TCD flow velocities are categorized as follows:

- 1. Normal: < 170 cm/sec
- 2. Conditional: 170 to < 200 cm/sec the eligible participant population for this study
- 3. Abnormal: \geq 200 cm/sec

Enrolled participants with TCD flow velocity values ≥ 200 but < 220 cm/sec may continue in the study and must have a repeat TCD within 2 to 4 weeks (timing based on Principal Investigator clinical judgement). If the repeat TCD flow velocity is abnormal, study drug will be discontinued (see Section 3.4.2 for information on discontinuation requirements) and the participant is required to return for the End of Study (EOS) visit (28 days after the last dose of study drug). Participants will be treated according to local standard of care for abnormal TCD flow velocity.

Enrolled participants with TCD flow velocity value of \geq 220 cm/sec will have study drug discontinued and return for the EOS visit (28 days after the last dose of study drug). Patients will be treated according to local standard of care for abnormal TCD flow velocity.

3.1.2. Dosing of Participants Between 2 Years and < 4 Years of Age

At least 15 participants from 2 years to < 4 years of age will be enrolled. Enrollment of participants < 4 years of age will be initiated after the DSMB has reviewed safety and PK data from at least 12 participants < 30 kg treated with voxelotor for at least 28 days. These data for at least 12 participants may be generated from any of the voxelotor studies.

3.1.3. Assessments

Assessments and procedures are described in Section 6 and in Appendix A, Appendix B, and Appendix C.

3.1.4. Data and Safety Monitoring Board

An independent DSMB will monitor the safety and conduct of the study. The responsibilities, and other details of the DSMB will be described in the DSMB Charter.

The DSMB will be comprised of medical and statistical representatives and may provide recommendations to the Sponsor regarding stopping or modifying the study.

Sites and their respective Institutional Review Boards (IRBs)/Ethics Committees (ECs) will be informed of the DSMB recommendations if the recommendations affect study participant safety and/or lead to changes to the study conduct.

3.1.5. Minimization of Bias

This study uses a double-blind, randomized, multi-center design to minimize bias.

3.2. Treatment

See Section 5 for voxelotor and placebo information.

3.3. Duration of Study Participation and of the Study

The duration of study involvement for an individual participant is expected to be approximately 105 weeks (See Section 3.1.1 for additional information regarding the study periods for this study).

The study will end when the last participant's last visit occurs.

3.4. Stopping Rules

3.4.1. Early Discontinuation of the Study

The Sponsor has the right to terminate this study at any time. Reasons for terminating the study may include, but are not limited to, the incidence or severity of TEAEs in this or other studies indicating a potential health risk to participants.

In any instance of early termination of the study, the Sponsor will notify, in writing, the Investigators, regulatory authorities, and IRBs/ECs and will specify the reason(s) for termination.

3.4.2. Early Discontinuation of Individual Participants

3.4.2.1. Withdrawal of Consent

Participants and/or their caregiver/legal representative will be informed that they are free to discontinue treatment or withdraw from the study at any time and for any reason. The Investigator must withdraw from the study any participant who requests to be withdrawn or whose caregiver/legal guardian requests withdrawal.

3.4.2.2. Early Discontinuation of Study Treatment

Participants may be discontinued from study treatment for any of the following reasons:

- · Participant is lost to follow-up
- Adverse event(s)
- Abnormal TCD flow velocity
- Discretion of the Investigator

- Discretion of the Sponsor
- Pregnancy

If a participant is discontinued from study drug at a scheduled visit, that scheduled visit will become the Early Treatment Discontinuation (ETD) visit and all required assessments for the ETD visit (see Appendix B) should be completed. The participant should then return to the study site for an EOS visit approximately 28 days after the last dose of study treatment as indicated in Appendix B.

If a participant is discontinued between scheduled visits, there is no requirement for an ETD visit. End of Study visit for such participants should be scheduled for 28 days after the last dose of study drug.

3.5. Randomization and Unblinding

3.5.1. Randomization

Randomization will be carried out through an Interactive Response System (IXRS). Permuted blocks within randomization strata will be used. Eligibility of the participant should be confirmed by the Investigator prior to randomization.

3.5.1.1. Preventing Unblinding Due to Laboratory Assessments

Because knowledge of certain laboratory assessments over time (Hb, hematocrit [Hct], RBC count, total and unconjugated bilirubin) may suggest the treatment assignment, these measurements will be redacted to the Investigator.

Results of redacted laboratory tests will be communicated to the Investigator if a participant's Hb declines to < 5.0 g/dL, or if the Hb declines $\geq 2 \text{ g/dL}$ from screening. This does not require breaking of the treatment assignment blind. This is to ensure participant safety by allowing the Investigator to monitor for worsening anemia which could require intervention (eg, due to a viral infection). Anonymized laboratory results will be available to the Sponsor.

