7.2.3. Abnormal Laboratory Values

Only clinically significant laboratory abnormalities will be recorded on the AE eCRF (eg, abnormalities that have clinical sequelae, require study drug dose modification, discontinuation of study treatment, more frequent follow-up assessments, further diagnostic investigation). If the clinically significant laboratory abnormality is a sign of a disease or syndrome (eg, ALK and bilirubin 5 × the ULN associated with cholecystitis), only the diagnosis (eg, cholecystitis) needs to be recorded on the eCRF.

If the clinically significant laboratory abnormality is not a sign of a disease or syndrome, the abnormality itself should be recorded on the eCRF. If the laboratory abnormality can be characterized by a precise clinical term, the clinical term should be recorded. For example, an elevated serum potassium level of 7.0 mEq/L should be recorded as "hyperkalemia."

Observations of the same clinically significant laboratory abnormality from visit to visit should not be repeatedly recorded on the AE eCRF, unless their severity, seriousness, or etiology changes.

Note: Potential drug-induced liver injury (DILI; Hy's law) cases are to be reported as SAEs (Section 7.3). For suggested actions and follow-up assessments in the event of potential DILI, refer to Appendix D. (This note is included to support Study transition to Pfizer Pharmacovigilance processes and systems.)

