In the majority of DILI cases, elevations in AST (aspartate transaminase) and/or ALT (alanine transaminase) precede total bilirubin elevations (> 2 × ULN) by several days or weeks. The increase in total bilirubin typically occurs while AST/ALT is/are still elevated above 3 × ULN (ie, AST/ALT and total bilirubin values will be elevated within the same laboratory sample). In rare instances, by the time total bilirubin elevations are detected, AST/ALT values might have decreased. This occurrence is still regarded as a potential DILI. Therefore, abnormal elevations in either AST OR ALT in addition to total bilirubin that meet the criteria outlined below are considered potential DILI (assessed per Hy's law criteria) cases and should always be considered important medical events, even before all other possible causes of liver injury have been excluded.

The threshold of laboratory abnormalities for a potential DILI case depends on the participant's individual baseline values and underlying conditions. Participants who present with the following laboratory abnormalities should be evaluated further as potential DILI (Hy's law) cases to definitively determine the etiology of the abnormal laboratory values:

- Participants with AST/ALT and total bilirubin values within the normal range who subsequently present with AST or ALT values ≥ 3 × ULN AND a total bilirubin value ≥ 2 × ULN with no evidence of hemolysis and an alkaline phosphatase value < 2 × ULN or not available.
- For participants with baseline AST OR ALT OR total bilirubin values above the ULN, the following threshold values are used in the definition mentioned above, as needed, depending on which values are above the ULN at baseline:

- Preexisting AST or ALT baseline values above the normal range: AST or ALT values ≥ 2 times the baseline values AND ≥ 3 × ULN; or ≥ 8 × ULN (whichever is smaller).
- Preexisting values of total bilirubin above the normal range: total bilirubin level increased from baseline value by an amount of ≥ 1 × ULN or if the value reaches ≥ 3 × ULN (whichever is smaller).

Rises in AST/ALT and total bilirubin separated by more than a few weeks should be assessed individually based on clinical judgment; any case where uncertainty remains as to whether it represents a potential Hy's law case should be reviewed with the sponsor.

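### Total bilirubin is hidden from the site with only hemoglobin-based release triggers, although the Hy's law reporting rule depends on it; first recognition is weakest when bilirubin rises shortly after ALT/AST have fallen

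*Protocol*

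**What the plan says.** **Redaction.** Protocol 3.5.1.1 lists the hidden results: "Hb, hematocrit [Hct], RBC count, total and unconjugated bilirubin) may suggest the treatment assignment, these measurements will be redacted to the Investigator". On release it says: "Results of redacted laboratory tests will be communicated to the Investigator if a participant's Hb declines to < 5.0 g/dL", or if Hb falls by 2 g/dL or more from screening. The stated purpose is to let the Investigator watch for worsening anemia. It adds: "Anonymized laboratory results will be available to the Sponsor". No reviewer, threshold, timing or duty to alert the site is given.

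**Liver reporting.** Section 7.2.3 says that potential Hy's law "cases are to be reported as SAEs (Section 7.3". Appendix D treats as potential drug-induced liver injury "abnormal elevations in either AST OR ALT in addition to total bilirubin that meet the criteria outlined below". From a normal baseline the limits are "AST or ALT values ≥ 3 × ULN AND a total bilirubin value ≥ 2 × ULN with no evidence of hemolysis", with alkaline phosphatase below 2 × ULN or not available. If bilirubin is already raised at baseline, the test becomes "total bilirubin level increased from baseline value by an amount of" at least 1 × ULN, or a value of at least 3 × ULN. Appendix D also describes a late pattern, which it calls rare: "by the time total bilirubin elevations are detected, AST/ALT values might have decreased. This occurrence is still regarded as a potential DILI".

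**Testing.** Section 6.12 routes laboratory work through a central laboratory, which is also preferred for repeats unless results are urgent. It makes the Investigator responsible for judging all abnormal values. Section 6.12.2 measures total, direct and indirect bilirubin.

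**The concern.** The protocol gives the Investigator a safety duty that turns on total bilirubin. A separate blinding rule withholds total bilirubin unless hemoglobin falls. The text does not say which rule gives way.

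Appendix D and the note in 7.2.3 state that they were included to support a change of pharmacovigilance systems. Appendix D also says that liver function tests are not routine monitoring in this study, although the chemistry panel contains them. Both points suggest that the liver rules were not reconciled with the redaction rule.

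At stake is timely recognition at the site of a possible liver injury in a child, and a complete count of such cases in the safety database.

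**Working it through.** The plan gives no figure to reproduce. The check sets the rules side by side and adds one piece of visit arithmetic.

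**1. When is bilirubin released?** The stated condition is Hb < 5.0 g/dL, or screening Hb minus current Hb ≥ 2 g/dL. Neither term contains ALT, AST or bilirubin. With Hb stable, no liver value of any size meets a stated release trigger.

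**2. What does the site see?**

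| Needed for Appendix D | Status under 3.5.1.1 |
|---|---|
| AST, ALT | visible |
| Alkaline phosphatase | visible |
| Total bilirubin, or its change from a raised baseline | redacted |
| Absence of hemolysis | LDH and reticulocytes visible; Hb and unconjugated bilirubin redacted |

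Direct bilirubin is not on the redaction list. Table 6 uses raised conjugated bilirubin as one of its signs of compromised liver function.

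**3. Which routes lead to recognition?**

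- *ALT raised at the sample.* From a normal baseline, Table 6 directs a repeat within 48 to 72 hours at ALT ≥ 3 × ULN, then at least weekly panels until ALT is improving. Appendix D asks for repeat total bilirubin in suspected cases. The site has a prompt. It remains unstated whether the total bilirubin from a central-laboratory repeat is shown to the site.
- *AST raised alone.* The Table 6 liver rows name ALT only. But AST is visible, and Appendix D asks for closer monitoring of any transaminase rise above 3 × ULN. The site has a prompt here too, so this is not a separate gap.
- *Bilirubin raised after ALT/AST have fallen.* The weekly panels may have stopped and no Table 6 ALT row is active. The total bilirubin that would show the case is redacted. What remains is visible direct bilirubin, symptoms or Sponsor action.

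**4. Does the visit schedule allow the third route?** SAP Table 1 puts Week 24 at Day 168 (window 161 to 175) and Week 28 at Day 196 (window 189 to 203).

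- Target gap: 196 − 168 = 28 days.
- Shortest: 189 − 175 = 14 days. Longest: 203 − 161 = 42 days.

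Appendix D says bilirubin typically follows by several days or weeks, and leaves rises separated by more than a few weeks to clinical judgment, with uncertain cases reviewed with the sponsor. A 14-day separation is plausibly inside the few weeks; 28 days is near the edge. From Week 36 on, target visits are 84 days apart (for example 336 − 252), so a rise first seen at one visit and bilirubin first seen at the next would fall to judgment. Those long gaps come from the schedule, not from the redaction. All of this assumes chemistry at each visit; that part of Appendix B is not readable.

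**5. Illustration.** Assume Hb 8.0 g/dL throughout and normal baseline liver tests. ALT is 4 × ULN on Day 175 and 1.5 × ULN on Day 182. On Day 189 total bilirubin is 2.5 × ULN, alkaline phosphatase is below 2 × ULN and there is no sign of hemolysis.

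- Release: 8.0 is not below 5.0, and 8.0 − 8.0 = 0 is less than 2. Not triggered.
- Table 6 ALT rows on Day 189: inactive if ALT has stayed at 1.5 × ULN.
- Appendix D late pattern: 189 − 175 = 14 days, and 2.5 exceeds 2. It merits evaluation as potential drug-induced liver injury.

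This shows that the rules permit the situation. It does not say how often it occurs.

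**6. Does the SAP look for it?** SAP 8.3.4 summarizes ALT, AST, total and direct bilirubin separately, with graded abnormalities and shifts. It names no joint transaminase-and-bilirubin display, and its chemistry list omits alkaline phosphatase. Table mock-ups are in a separate document not seen here.

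**The case against.** The strongest reply is that redaction affects first recognition only. Appendix D attaches the reporting duty to cases confirmed on repeat testing with no other cause found, so a further test is needed with or without redaction. That work-up names total, direct and indirect bilirubin, and Section 6.12 allows non-central testing when results are urgent. Hiding the hemolysis-related fraction while leaving conjugated bilirubin visible is a coherent blinding choice. The Sponsor holds the results and may request repeats. A DSMB monitors safety, and its Charter or a laboratory manual may contain an alert.

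Most of this stands. A reader might infer that the site cannot detect Hy's law cases at all, or that rises in AST alone go unnoticed. The documents support neither: the transaminases and direct bilirubin are visible, and both Table 6 and Appendix D act on raised transaminases.

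Two things survive. Direct bilirubin can prompt a test, but the Appendix D limits are written in total bilirubin, including its change from a raised baseline. And no text exempts central-laboratory repeats from redaction or makes anyone responsible for alerting the site. An unseen charter or manual might do so, but the available text does not show that it does.

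On the SAP, the reply is fair. A joint display would be a useful check; its absence is not an error.

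**Conclusion.** The concern holds in limited form. The stated release triggers are all hemoglobin-based, while a stated safety duty depends on total bilirubin, and the protocol does not reconcile the two. The practical weakness is in initial recognition. It is greatest when bilirubin rises within a few weeks after ALT/AST have fallen, which the protocol itself calls rare.

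Severity is minor to moderate. No number of missed cases can be derived from the documents. The conclusion assumes stable Hb, redaction applied as 3.5.1.1 is written, and no liver alert in documents not seen.

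A reader might connect this with the safety imbalance that led to the dosing pause (SAP Introduction). The documents do not say that the imbalance was hepatic, and nothing here shows that a case was missed.

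**What to change.** **Protocol wording, for any study that reuses this redaction rule.** In 3.5.1.1, state that total and direct bilirubin go to the Investigator, or that a named role with unredacted data alerts the site, when either:

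- AST or ALT meets the Appendix D threshold (≥ 3 × ULN, or the baseline-adjusted equivalent); or
- total bilirubin meets its Appendix D threshold within a set few weeks after such a rise.

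State also that repeat tests for suspected Hy's law are not redacted. The cost is wording and a central-laboratory alert setting. The downside is that a few bilirubin values become visible to a site; routing the alert through the named role would reduce this.

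**This trial.** Dosing was paused on 1 May 2024 and the study was later terminated, so the wording can no longer help participants. SAP 6.3 plans a final analysis after database lock. Add to SAP 8.3.4 a by-arm retrospective screen of stored AST, ALT, total and direct bilirubin and alkaline phosphatase against the Appendix D thresholds. Count same-sample cases and bilirubin-after-transaminase cases separately, show hemolysis measures alongside, and reconcile the result with reported serious adverse events. Keep the table within the SAP 8.3 limit of 28 days after last dose and put later values in a listing. The cost is one table and one listing from data already held, with no patient procedures.

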3.5.1.2. Unblinding for Medical Need

If a medical condition should arise for which appropriate treatment cannot be decided without knowledge of the study treatment assignment, the Investigator may unblind a study participant. The Investigator should promptly document and notify the Sponsor of any premature study treatment unblinding (eg, accidental unblinding, unblinding due to a treatment-related SAE). Pregnancy is considered an event that requires unblinding. Unblinding procedures specified in the IXRS Manual will be followed and documented in the Investigator site file.

3.5.1.3. Unblinding for Pharmacokinetic Analysis

To facilitate the PK analysis, the bioanalytical laboratory and the contract research organization (CRO) analyzing the PK/PD data will be unblinded to treatment assignments during the study. Interim analysis may be performed and data summarized per treatment arm; however, the blinded Sponsor study team will not be unblinded to individual treatment assignment.

